## 1.0 Study Summary

Study Title	Comparative effectiveness trial of clinic-based delivery of an HIV risk reduction intervention (YMHP) for YMSM, Phase 2
Study Design	Comparative Effectiveness Trial (CET), Randomized Control trial (RCT)
Primary Objective	The purpose of this study is to adapt and test the effectiveness of the Young Men's Health Project (YMHP) at three subject recruitment venues (SRVs) within the Adolescent Medicine Trials Network for HIV/AIDS Interventions (ATN), in an effort to reduce HIV and STI disparities among urban young men who have sex with men (YMSM). We will conduct a comparative effectiveness trial to compare the effectiveness of the YMHP intervention delivered via two modalities – clinic-based versus remote delivery – following HIV counseling and testing (HIV C&T).
Secondary Objective(s)	To examine differences in effectiveness and cost by method of delivery, and to use our observations about the implementation of YMHP to improve portability and scalability. The study will also help us better understand HIV-prevention focused self-management behaviors among HIV-negative YMSM.
Research Intervention(s)	We are comparing two modalities for the delivery of the YMHP – clinic-based versus remote. YMHP consists of four sessions during which youth choose which particular behaviors (sexual risk or substance use) to discuss. The community health work (CHW) elicits the client's view of the problem using standard motivational interviewing (MI) techniques, building motivation for change by eliciting and reinforcing change talk and clarifying the youth's own personal priorities (through a structured values card sort activity). The CHW will discuss options for a behavior change plan, and, if the client is willing to proceed, the client sets goals. Starting 10/15/19- comparing YMHP (participants chooses modality for delivery as clinic-based or remote) versus HIV testing and counseling standard of care.
Study Population	Adolescent age (15-24 years) HIV-negative YMSM
Sample Size	Phase 2 N = 180
Study Duration for individual participants	Phase 2: 15 months, Starting 10/15/19- 12 months
Study Specific Abbreviations/ Definitions	Adolescent Medicine Trials Network (ATN) Condomless anal sex (CAS) Comparative Effectiveness Trial (CET) Community health worker (CHW) HIV counseling and testing (HIV C&T) Motivational interviewing (MI)

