Secondary Aim: The design will result in a subsample of youth who were randomized to receive YMHP in a clinic-based or remote delivery. It will also yield a subsample who are allowed to self-select delivery method. We will utilize these subsamples to assess youth preferences for

PROTOCOL TITLE: Comparative effectiveness trial of clinic-based delivery of an HIV risk reduction intervention (YMHP) for YMSM, Phase 2

delivery format, evaluate whether delivery format is associated with session retention, and test for any indications that delivery format is associated with response to intervention.

We will achieve our aims over 2 phases of the study.

Phase 1: We conducted focus groups with youth as part of our formative research to obtain implementation feedback about the delivery of the YMHP intervention and intervention components to ensure culturally competent, feasible, and scalable implementation both in the clinic setting and via remote delivery. Feedback from these focus groups at the 3 SRVs has been used to modify the YMHP intervention prior to the launch of Phase 1. Phase 1 focus groups were conducted with youth at each of the 3 SRVs to gather information that would be used to better implement YMHP. Groups were broken down into two age groups, 15-17 and 18-24.

We will train a minimum of 2 CHWs at each SRV to deliver the YMHP sessions, who must demonstrate competence according to the Motivational Interviewing Treatment Integrity (MITI) before providing the intervention in Phase 2.

Phase 2: We will recruit and enroll 270 YMSM, aged 15-24, 90 at each of the 3 SRVs. Enrollment will be limited to HIV-negative YMSM who report recent substance use and either CAS or a positive STI test result. Participants will be randomized to receive a standard of care enhanced HIV testing and counseling versus the YMHP intervention in person or by remote delivery (initial in-person session). The modality of delivery is chosen by the participant and involves completion of the 4 YMHP sessions and the delivery of pre-exposure prophylaxis (PrEP) information and navigation services to interested participants. Fidelity will be monitored throughout the trial. Sessions will be audio-recorded for MITI fidelity coding, and CHWs and supervisors will be given implementation support throughout the study period.

The current application is for Phase 2; Phase 1 has already been complete.

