### **Randomization**

Participants will be randomized after completing the baseline assessment (i.e., CASI and specimen collection), but prior to their first YMHP session. Participants are randomized into one of two intervention conditions: 1) YMHP (delivery of the YMHP intervention in person or

**PROTOCOL TITLE:** Comparative effectiveness trial of clinic-based delivery of an HIV risk reduction intervention (YMHP) for YMSM, Phase 2

remotely), or 2) a standard of care HIV Testing and counseling session with referrals to other available services. . If the participant is randomized to YMHP, the first YMHP session will always be conducted in person after the baseline assessment. In the event a participant does not wish to complete the first YMHP session immediately after the baseline assessment, the SRV will postpone the participant's randomization. Randomization will then occur when the participant returns to the SRV for their first YMHP session. If the participant is randomized to HIV Testing, no additional intervention procedures are required, because HIV testing is conducted in conjunction with the Baseline appointment. However, the CHW will meet with the participant to ensure that any individual risk assessment is administered and referrals for PREP and other prevention services are given consistent with clinic standards of care for individual HIV testing.

**COVID accommodations-** In the event the baseline visit is conducted virtually (see below for details), randomization will still occur after HIV Testing and before the intervention. Since many individuals who are randomized to HIV testing only will have already received that portion of the appointment, randomization may occur before scheduling session 1.

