## **12.0 Local Number of Subjects**

Anticipated enrollment: 270 YMSM

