## **25.0 Multi-Site Research**

This research is being conducted at Wayne State University Prevention (W'SUP) at Wayne State University in Detroit, MI, the University of Miami Division of Adolescent Medicine in Miami, FL, and the Children's Hospital of Philadelphia (CHOP) Division of Adolescent Medicine in Philadelphia, PA.

Each site will enroll 60 individuals.

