1.2 Quantitative Analysis Plan

The primary hypothesis is that receipt of YMHP (regardless of delivery format) will be associated with greater improvements in sexual health management (as measured by decreased STIs, CAS and increased PrEP uptake/adherence) as well as greater reductions in substance use, compared with youth who receive the standard of care (individual HIV testing) only. Our secondary hypothesis is that youth who elect to receive YMHP remotely will report more barriers to accessing health care compared to those who elect to receive the intervention in clinic. In addition, we hypothesize that remote-based YMHP will demonstrate greater improvements in sexual health management (as measured by decreased STIs, CAS, and increased PrEP uptake/adherence) as well as reductions in substance use, compared to clinic-based YMHP, among YMSM who do report barriers to health care access. In contrast, it is hypothesized that clinic-based YMHP will demonstrate greater improvements in sexual health management and reduced substance use among YMSM who do not report barriers to health care access. Self-management model analysis is described in the AC.

The AC will test the effect of clinic-based versus remote delivery on STI rates, alcohol and drug use behavior, CAS, and PrEP uptake through multi-level growth mixture modeling (GMM). A separate model will be run for each outcome. Each model will be a 2-level model in which individuals (Level I) are nested in clinics (Level II). This approach controls for the non-independence of individuals within clinics. Because three SRVs provide extremely limited predictive power at Level II, no site covariates are included in the model. (The models are empty at Level II).

In a GMM, a latent growth curve with an intercept and linear slope factor is specified. Latent class analysis is applied to these 2 growth components (intercept and slope) to identify groups of individuals who share trajectories. For example, with regard to drug or alcohol use, “immediate and sustained responders” may have the lowest post-intervention intercept and a flat slope. Meanwhile, “non-responders” might have the highest post-intervention intercept and a flat slope. In contrast, “delayed responders” might have a high post-intervention intercept but a significant negative slope, indicating reductions in missed medication over the follow up period.

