1.2.1 Power Analysis

First, we analyzed power assuming independence of participant observations (assuming that the nesting of people-within-clinic was irrelevant). With regard to STIs, we utilized the “repeated measures” module of PASS 13.0 to examine power to detect odds ratio differences in a repeated measures design. Specifying compound symmetry, we allowed ρ to vary between .2 and .5. Assuming the prevalence of STIs in the remote-based condition varies between .05 and .15, the proposed design ($N = 270$) has power .80 to detect an odds ratio of .20 to .50. Similarly, with regard to the odds of PrEP uptake, allowing the rate of uptake in the remote-based condition to vary between .05 and .20 and allowing ρ to vary between .4 and .7, the proposed design has power of .80 to detect an odds ratio of 1.9 to 2.3. With regard to number of alcohol and drug use days, we utilized the *Tests for Two Poisson Means* module in PASS 13.0. Based data from our previous studies, we allowed the rate of heavy drinking in the phone-based condition to vary between 7 and 9 days during a 30-day assessment. The study is adequately powered to detect a 3% reduction in number of heavy drinking days in the clinic-based condition at any single follow up point. Allowing the rate of drug use in the remote-based condition to vary between 3 and 5 days during a 30 day assessment period, the study is adequately powered to detect a 4% reduction in drug use in the clinic-based condition. A similar analysis was conducted with respect to CAS. Based on our previous research, we allowed the rate of CAS in the phone-based condition to vary between 2 and 4 acts in a 30 day assessment period. The study is powered to detect a difference as small as 5% between the remote and clinic-based YMHP conditions. The nesting of individuals within SRVs has the potential to reduce power because substantial variability in outcome across SRVs can obscure level II treatment effects [70, 71]. The design effect can be used to tailor power analyses calculated under assumptions of independence. In the case of a Level I predictor with a fixed effect which is uncorrelated with other covariates in the model, the design effect is equal to the $1 - \rho$, where ρ is the intra-class correlation or the percentage of variance accounted for by variability between SRVs [71]. In previous intervention trials conducted within the ATN [72], between clinic site variability in HIV related outcomes did not differ significantly from zero. Based on the characteristics of ATN clinics, we anticipate a similar absence of variability across clinics, suggesting that the design effect would result in a negligible reduction in power. Finally, a sample size of 270 is sufficient to detect a moderation effect with an f^2 of .02. Cohen [73] designates this as a small effect, however recent work has characterized an effect of this size as moderate to large as applied to moderation [74].

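### Phase 2 is sized at 180 in two protocol sections and at 270 in two others and the SAP, and the SAP's claim that 270 suffices for moderation has no stated basis

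*SAP*

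**What the plan says.** **Planned size.** The sample-size row of the Study Summary (Protocol 1.0) gives 180 for Phase 2. Protocol 25.0 says "Each site will enroll 60 individuals" and lists three sites. Protocol 2.0, under Phase 2, says "We will recruit and enroll 270 YMSM, aged 15-24, 90 at each of the 3 SRVs". Protocol 12.0 says "Anticipated enrollment: 270 YMSM". SAP 1.2.1 uses 270.

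**Moderation.** SAP 1.2.1 ends with the statement that "a sample size of 270 is sufficient to detect a moderation effect with an f^2 of .02". The secondary hypothesis in SAP 1.2 is that remote YMHP does better, "compared to clinic-based YMHP, among YMSM who do report barriers to health care access", and that clinic-based YMHP does better among those without barriers.

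**Who receives YMHP.** From 10/15/19 the Study Summary describes the trial as "comparing YMHP (participants chooses modality for delivery as clinic-based or remote) versus HIV testing and counseling standard of care". Protocol 6.0 (Randomization) says "Participants are randomized into one of two intervention conditions": YMHP, or standard-of-care HIV testing and counseling. The Secondary Aim in Protocol 2.0 also refers to participants allocated by format: "The design will result in a subsample of youth who were randomized to receive YMHP in a clinic-based or remote delivery".

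**The concern.** A trial needs one planned size. Here the total and the per-site number each take two values in current text, and power is computed at only one of them. If 180 is the plan, every power statement in SAP 1.2.1 is for a trial half as large again.

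The moderation sentence raises a second question. An f-squared of .02 is small for 270 people, and the sentence does not say what test, error rate or power lies behind it. If the format-by-barriers interaction is under-powered but described as adequately sized, a null result could be misread as evidence that access barriers do not matter to the choice of format.

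**Working it through.** **1. The two totals.** 3 × 60 = 180 agrees with Protocol 1.0. 3 × 90 = 270 agrees with Protocol 2.0, 12.0 and the SAP. Protocol 1.0 and 2.0 both attach their figure to Phase 2, so a split between Phase 1 and Phase 2 does not explain the difference.

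**2. What the difference costs.** For any effect with 80% power at 270 (two-sided 5%), power at 180 by the normal approximation is

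Φ((1.960 + 0.842) × √(180/270) − 1.960) = Φ(0.328) = 0.628.

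**3. The moderation claim.**

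- From SAP 1.2.1: f² = .02 and N = 270.
- Carried over from the STI and PrEP sentences of SAP 1.2.1: power of .80. None is given for moderation.
- Assumed, because not stated: a 1-df interaction (two-level condition by any or no barrier), alpha .05 two-sided, one measure per person, everyone contributing and no dropout.

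Method: noncentral F with df1 = 1, df2 = N − 4 and noncentrality λ = f² × N. At N = 270, λ = .02 × 270 = 5.4. At N = 180, λ = 3.6.

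| Basis | N = 270 | N = 180 | N for 80% |
|---|---|---|---|
| Two-sided 5% | 63.9% | 47.1% | 395 |
| One-sided 5% | 75.0% | 59.7% | 311 |

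The normal approximation agrees: Φ(√5.4 − 1.960) = Φ(0.364) = 0.642 at 270. Between 1 and 10 predictors the result does not change materially. Reaching 80% at 270 on this basis would need a two-sided alpha of about .14. The f² detectable with 80% power, two-sided, is .029 at 270 and .044 at 180. So *sufficient* is not reproduced at .80 on a single-measure basis.

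**4. Repeated-measures sensitivity.** If f² is a per-visit effect and M follow-ups with within-person correlation ρ are averaged, λ is multiplied by M/(1 + (M − 1)ρ). Taking M = 4 and ρ = .5 (assumptions), the factor is 4/2.5 = 1.6:

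- Power for f² = .02 is 83% at 270 and 67% at 180.
- 80% needs 248.
- The detectable f² falls to about .018 at 270 and .028 at 180.

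Across M = 2 to 4 and ρ = .2 to .7 (the span of correlations that the SAP uses for STI and PrEP), power at 270 runs from about 71% to 96%.

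**5. Who informs the contrast.** Standard-of-care participants have no delivery format during the comparison, so a remote-versus-clinic contrast rests on YMHP recipients. Their number appears nowhere. On the step 4 basis (M = 4, ρ = .5), 270 − 248 = 22: once more than 22 of 270 participants do not inform the contrast, power is below 80%.

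**The case against.** **A cohort split could reconcile the totals.** The revision history mentions a Cohort 1, and the Study Summary dates a design change, so 180 and 270 might describe different cohorts. That is possible, but no section says so, and Protocol 2.0 describes all 270 under the YMHP versus standard-of-care randomisation. Stating the relation would be an acceptable fix.

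**The 64% does not prove an arithmetic error.** This stands. A reader might infer that the SAP miscalculated. It states no alpha, power, sidedness or degrees of freedom for moderation, so there is no calculation to contradict. The planned models are longitudinal (growth factors or trajectory classes), and the same section uses a repeated-measures module for STIs, so a single-measure regression is not clearly what was meant. A linear f² test only approximates those models, although f² is the SAP's own metric.

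**Nor is 64% a ceiling, or .029 the best attainable.** This also stands: one-sided testing gives 75%, and averaging visits can pass 80%. Three limits apply. The SAP states no such basis for moderation. The gain assumes that all 270 contribute. STI testing is scheduled at only two follow-ups (3 and 9 months), so four-visit averaging is not available for that outcome. If f² is defined on a person-level growth factor, there is no gain at all.

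**Who contributes is partly open.** SAP 1.2 specifies a condition-by-barriers interaction without saying whether condition means delivery format or YMHP versus standard of care. The hypothesis itself names format. It is tempting to assume 1:1 allocation and quote a much lower power, but neither the allocation ratio nor the size of any format-randomised cohort is stated.

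**Site targets.** A reader might infer that sites are recruiting to different targets. The documents show conflicting text, not what sites are using.

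**Conclusion.** The conflict on planned size is explicit and needs no assumption: 180 in Protocol 1.0 and by implication 25.0, against 270 in Protocol 2.0, 12.0 and the SAP. It matters to the whole trial, because an effect with 80% power at the larger figure has about 63% at the smaller. This part carries the weight of the point.

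The moderation claim is unsupported as written, not shown to be wrong. On a 1-df, two-sided 5%, single-measure test with all participants contributing, power is about 64% at 270 and 47% at 180, short of the .80 used elsewhere in the section. Whether a repeated-measures basis would rescue it depends on the number of visits, the correlation and the number of YMHP recipients, none of which is stated for this test. That number is below the total if any participants counted in it are randomised to standard of care.

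The moderation sentence concerns only the secondary hypothesis. The unresolved N also bears on the primary YMHP versus standard-of-care comparison, for which SAP 1.2.1 offers no calculation: where it names a contrast, it is remote or phone versus clinic-based delivery.

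**What to change.** 1. State one N and the matching per-site number in Protocol 1.0, 2.0, 12.0, 25.0 and the SAP, or state how 180 and 270 relate (for example by cohort).
2. Re-run the SAP 1.2.1 calculations at that N and add the YMHP versus standard-of-care contrast. Re-running the existing calculations alone would leave the primary hypothesis without a power statement.
3. For moderation, state alpha and sidedness, degrees of freedom, the expected number of participants who inform the contrast, and any repeated-measures assumption (number of measures and correlation).
4. Replace *sufficient* with the resulting power for f² = .02, or with the f² detectable at 80%. On the single-measure, two-sided 5% basis with everyone contributing, that is .029 at 270 or .044 at 180.

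The cost is wording in four protocol sections and the SAP, plus a power re-run. No extra enrolment is needed. The downside is a possibly less favourable stated power for the secondary hypothesis.

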
1.2.2 Equivalency Checks

The AC will ensure that randomization is stratified by city and the presence of any barriers to healthcare access. Further, they will monitor randomization to ensure that condition is not associated with characteristics that would require adjustment in proposed analyses. To assess differential attrition, we will utilize a multilevel modeling approach (to account for the nesting of participants within clinic/city) to assess for condition, time, and condition \times time interaction effects in the proportion of completed assessments across the length of follow-up. Any evidence of differential attrition will be examined to determine whether there are baseline demographics, behavioral, or biological predictors that are associated with such differences in attrition. These effects will be adjusted for in subsequent analyses.

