1.0 DATA MANAGEMENT AND ANALYSIS PLAN

1.1 Data Management and Data Quality

The SIU MC will be handling data management for the randomized controlled trials in a standard manner including scale scores, composites, syntax, etc. in order to facilitate rapid analyses by the AC. Data will be entered directly by participants through Qualtrics using systems established by the REC. Data dictated by participants who request assistance completing surveys may also be entered by the site RA. The database, data structure, and data quality will be routinely reviewed by the REC with support from the AC. Where indicated, we will use full-information maximum likelihood estimation to account for missing data under missing at random assumptions.

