If modeling results indicate that discrete classes are not present, we will proceed with analyses in which the growth factors (intercept and slope) are predicted directly by intervention condition (and demographic factors found to be associated with condition after randomization or with attrition over follow up). GMMs can subsequently incorporate predictors of class membership. These analyses can be conceptualized as a multi-nominal logistic regression with the latent trajectory-class membership constituting the outcome. The predictors

of primary interest will be intervention condition, the presence of any barriers to health care access, and the interaction between condition and barriers to access. We will include as covariates any demographic variables that were associated with condition after randomization or with attrition over the follow up period.

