1.2.3 Equivalency Tests

A series of bivariate analyses will be conducted to examine between condition differences at baseline and evaluate

the success of randomization procedures. We will utilize chi square tests of independence, t-tests, ANOVA and Spearman's rho correlations as appropriate to examine whether intervention conditions differed significantly with respect to key demographic variables and outcome variables at baseline. In the event that significant baseline differences are observed, these demographic factors will be incorporated into subsequent outcome analyses.

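### Baseline behavioural and biological predictors of dropout enter the outcome models only if completion is found to differ, and that check cannot see different people leaving each arm at equal rates

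*SAP*

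**What the plan says.** SAP 1.2.2 (Equivalency Checks) fits a multilevel model for condition, time and condition-by-time "interaction effects in the proportion of completed assessments across the length of follow-up". The next step depends on the result: "Any evidence of differential attrition will be examined to determine whether there are baseline demographics, behavioral, or biological predictors that are associated with such differences". The section's closing sentence reads: "These effects will be adjusted for in subsequent analyses". No significance level or other threshold is given for what counts as evidence.

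Three other places bear on the same question.

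- SAP 1.2 (Quantitative Analysis Plan), class-membership model: "We will include as covariates any demographic variables that were associated with condition after randomization or with attrition over the follow up period". No arm difference is required, but only demographics are covered. The fallback growth model has the same limit: "demographic factors found to be associated with condition after randomization or with attrition over follow up".
- SAP 1.2.3 (Equivalency Tests) compares outcome variables as well as demographics at baseline, but carries forward only the latter: "In the event that significant baseline differences are observed, these demographic factors will be incorporated into subsequent outcome analyses".
- SAP 1.1 says that, where indicated, "we will use full-information maximum likelihood estimation to account for missing data under missing at random assumptions". It names no auxiliary variables.

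SAP 1.2 does not say whether the baseline outcome is a time point in the growth curve. Its illustrations describe an intercept measured after the intervention.

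**The concern.** Full-information maximum likelihood (FIML) protects against selective dropout only through variables that are in the model. If heavier substance users are more likely to leave, baseline use has to be there, as a covariate, an auxiliary variable or a time point. The SAP makes the search for such predictors depend on a comparison of how many people complete, not of who completes.

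That comparison can fail in two ways. It may lack power for a modest gap in completion. And if the arms lose equal numbers of different people, there is no gap to find.

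The second case is plausible here, although the documents do not show that it occurs. Under Protocol 6.0, YMHP participants are asked to attend four sessions on sexual risk and substance use. Controls attend no further sessions and are offered YMHP after the 9-month follow-up. For remote baseline visits, payment in the YMHP arm waits until Session 1 is done. At stake is the primary contrast, YMHP versus standard of care.

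**Working it through.** The documents give no expected attrition, no threshold for the check and no power for it, so there is no planned figure to reproduce.

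**Inputs from the documents.** Two arms (Protocol 6.0, Randomization). Four assessments after baseline (Protocol 9.0). Sample size 270 (Protocol 2.0 and 12.0, SAP 1.2.1) or 180 (Protocol 1.0; Protocol 25.0, 3 sites × 60). Both sizes are used below.

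**Assumptions.** 1:1 allocation, so n = 135 or 90 per arm; two-sided 5% test; within-person correlation ρ of completion from .3 to .7; completion rates as shown.

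**Step 1: power of the completion check.** Averaging four visits multiplies the variance by DE = (1 + 3ρ)/4, which is 0.475 at ρ = .3 and 0.775 at ρ = .7. Then SE = √[DE × (p₁q₁ + p₂q₂)/n] and power ≈ Φ(difference/SE − 1.96).

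For 80% versus 70%, p₁q₁ + p₂q₂ = 0.16 + 0.21 = 0.37.

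- n = 135, ρ = .3: SE = √(0.475 × 0.37/135) = 0.0361; power = Φ(2.77 − 1.96) = 0.79.
- n = 135, ρ = .7: SE = √(0.775 × 0.37/135) = 0.0461; power = Φ(2.17 − 1.96) = 0.58.
- n = 90, ρ = .3: SE = 0.0442; power = Φ(2.26 − 1.96) = 0.62.
- n = 90, ρ = .7: SE = 0.0564; power = Φ(1.77 − 1.96) = 0.43.

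The 10-point gap is therefore missed in 21–42% of trials at N = 270 and in 38–57% at N = 180. For 80% versus 75%, power is 20–30% and 15–21%. For 80% versus 65% it is 88–98% and 73–91%, so gaps of 15 points are mostly found.

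**Step 2: equal rates, different people.** Simulated trials with no true effect (2,000 to 4,000 per setting, depending on the run). Unless a row says otherwise, 25% drop out in each arm. The log-odds of dropout rise by a set slope per SD of baseline use in YMHP and by 0 in control. Correlation is .6 between baseline and each follow-up and among follow-ups. The completion check flags about 5% of such trials, which is only its own false-positive rate, so the rule as written nearly always leaves the baseline predictor out. Ranges are across separate runs.

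| Setting | Bias, favouring YMHP | False positives, N = 270 | False positives, N = 180 |
|---|---|---|---|
| Slope 1, dropouts miss all four follow-ups, baseline not in model | about 0.13 SD | 17–19% | 13–15% |
| As above, slope 0.5 | smaller | about 9% | about 8% |
| Slope 1, 35% lost per arm | larger | 26–27% | 20–21% |
| Slope 1, exits spread over the four visits, likelihood analysis of all observed visits, baseline not in model | about 0.04 SD | about 6–7% (one run 5.0%) | about 6–7% (one run 5.9%) |
| Slope 1, either exit pattern, baseline as a time point | about 0 | 4–6% | 4–6% |
| Same selection in both arms (slope 0.7 each, 20% or 30% lost, correlation .5), baseline not in model | about 0 | 5–6% | 4–6% |

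The fourth row is much milder than the first because people who leave late still contribute their early visits, and those visits carry much of the information about baseline risk. The fifth row shows what fixed inclusion of the baseline value achieves.

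**The case against.** The strongest reply is that the SAP specifies growth models with FIML, not an analysis of completers. If exits are gradual, the observed visits remove most of the bias even without the baseline value. If the baseline outcome is a time point, they remove all of it in these scenarios. The plan never says that baseline is excluded. This stands, and it limits the size of the point. It does not settle it. The SAP leaves the role of baseline open, and it runs a separate model per outcome, so baseline substance use would still be absent from the STI, CAS and PrEP models.

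Second, the SAP acts on any evidence and sets no alpha, and its check includes a time effect. A looser threshold, or a reading in which falling completion alone counts, would open the search more often. The miss rates in step 1 therefore depend on the assumed 5% test. Yet no threshold makes a comparison of proportions sensitive to equal-rate loss of different people.

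Third, participants who refuse sessions stay in follow-up (Protocol 14.0), which weakens the link between session burden and loss. That is fair; differential selection is a possibility, not a finding.

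Fourth, the plan already handles part of this. Demographic predictors of attrition enter without the condition. Barriers to care are a predictor in the class model and a stratification factor. City is a stratification factor, and clinic is the clustering level. The gap is confined to behavioural and biological baseline variables.

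Two stronger readings are tempting. A reader might infer from the section headings that a negative check is taken as proof that dropout is harmless; the SAP nowhere says so. A reader might also infer that balanced but selective attrition always inflates false positives to several times 5%. That needs strong selection in one arm, dropouts who miss every follow-up, and baseline outside the model.

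**Conclusion.** The point holds in a limited form. The SAP conditions adjustment for baseline behavioural and biological predictors of dropout on a check that has limited power for completion gaps of 5 to 10 points and cannot see equal-rate dropout of different people. Bias in the primary contrast can then remain, provided that dropout depends on baseline risk differently by arm and that the baseline outcome is not in the model.

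Under the assumptions above, the effect runs from none (same selection in both arms, or baseline in the model), through about 0.04 SD with 6–7% false positives (exits spread over visits), to about 0.13 SD with 13–19% (strong selection, all follow-ups missed). Dropout rate, selection strength, correlations, alpha and allocation ratio are all assumed, because the documents give none of them. The SAP should be changed mainly because the remedy is cheap and uses data already collected, not because large bias has been shown.

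**What to change.** Drop the condition in SAP 1.2.2 and state in SAP 1.2 that:

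1. every outcome model includes the baseline value of its outcome, as a covariate or time point. For PrEP uptake this carries little information, because Protocol 10.0 excludes current users of Truvada as PrEP, so item 2 matters most there;
2. every outcome model uses FIML with baseline substance use, CAS and STI status as covariates or auxiliary variables, whatever the attrition check shows, in addition to the barriers, city and demographic terms already in the plan;
3. the completion comparison is kept as description, reported as a difference with a 95% confidence interval;
4. the missingness model adds these baseline predictors and their interactions with condition, so that different people leaving each arm can be seen even when rates match.

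The baseline survey, STI tests and drug test are already collected (Protocol 6.0). The cost is SAP wording and a few extra parameters per model.
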